7.4 Dose Adjustments Due to Adverse Events

Clinical testing to date has revealed adverse events that may require temporary interruption of the study drug and/or a reduction in study drug dose. Modification of study drug administration may be required under the following circumstances:

- Increases in ALT, AST, or bilirubin (refer to [Appendix 1](#) for guidance regarding LFT-related dose adjustments).
- ANC < 1000/mm³ or 1.0 x 10⁹/L (refer to [Appendix 2](#) for guidance regarding management of neutropenia).
- Severe diarrhoea (refer to [Appendix 3](#) for guidance regarding diarrhoea-related dose adjustments).⁽⁶⁾
- Hypertension uncontrolled by oral antihypertensive medications (refer to [Appendix 4](#) for guidance regarding hypertension-related dose adjustments).
- Other severe or life-threatening adverse events considered related to study drug administration.

Subjects who have their dose reduced will not have their dose increased for the remainder of the study. When dose interruption or reduction is required, subjects and study staff will remain blinded to the original treatment allocation; however, subjects and study staff will be aware of the switch to a reduced dose level.

Subjects for whom dose reduction results in a once daily dose of fostamatinib or matching placebo will take the daily study drug dose in the morning. Table 4 details the strategy for dose adjustment in subjects who experience AEs requiring dose reduction.

Table 4: Dose Adjustment

Starting Dose	Dose Level -1	Dose Level -2	Dose Level -3 ^a	Dose Level -4 ^a
100 mg PO bid	150 mg PO qd	100 mg PO qd	Discontinue	-----
150 mg PO bid	100 mg PO bid	150 mg PO qd	100 mg PO qd	Discontinue

^a The Sponsor's Medical Monitor should be consulted prior to consideration of dose modification to levels -3 or -4.

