- When the ALT/AST or total (and/or conjugated) bilirubin returns to $< 1.5x$ ULN, study drug may be restarted at dose level -1.

If AST or ALT $\geq 3x$ ULN or total (and/or conjugated) bilirubin $> 2x$ ULN and subject is asymptomatic:

- Complete the appropriate LFT module of the CRF with the original laboratory test result.
- Repeat LFTs, including bilirubin and ALP, within 72 hours.
- If repeat testing shows an increase in ALT/AST or total (and/or conjugated) bilirubin and the ALT/AST value exceeds $5x$ ULN, hold dosing with the study drug.
- Repeat LFTs, including bilirubin and alkaline phosphatase every 3 days/72 hours until ALT/AST is decreasing, and should be followed until transaminase returns to $< 1.5x$ ULN.
- In subjects for whom study drug is interrupted, upon return of ALT/AST or total (and/or conjugated) bilirubin to $< 1.5x$ ULN, study drug may be restarted at dose level -1.

REFERENCES

FDA Guidance for Industry (issued July 2009) 'Drug-induced liver injury: Premarketing clinical evaluation':

<http://www.fda.gov/Drugs/GuidanceComplianceRegulatoryInformation/Guidances/ucm006499.htm>

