Appendix 2: Guideline for Management of Neutropenia

Based on data from previous clinical studies, treatment with fostamatinib may be associated with lowering of absolute neutrophil count (ANC).

A decrease in ANC may require adjustment of the dose of study drug. Follow the dose adjustment guidelines in Table 1 and outlined below when adjusting the dose of study medication.

Table 1: Dose Adjustment

Starting Dose	Dose Level -1	Dose Level -2	Dose Level -3 ^a	Dose Level -4 ^a
100 mg PO bid	150 mg PO qd	100 mg PO qd	Discontinue	-----
150 mg PO bid	100 mg PO bid	150 mg PO qd	100 mg PO qd	Discontinue

^a The Sponsor's Medical Monitor should be consulted prior to consideration of dose modification to levels -3 or -4.

Decrease in absolute neutrophil count (ANC) to < 1,000/ μ L:

- Repeat ANC within 72 hours in the local laboratory.
- If repeat testing confirms that ANC is < 1,000/ μ L, hold study drug dosing.
 - Repeat ANC at 72 hour intervals.
- When ANC recovers to > 1,500/ μ L, restart study drug at dose level -1.

Second event of ANC < 1,000/ μ L:

- Confirm ANC as above.
- If confirmed, hold study drug until ANC > 1,500/ μ L.
- Restart study drug at dose level -2.

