Appendix 4: Guideline for Management of Hypertension

Treatment with fostamatinib may cause blood pressure elevation in certain subjects. It is believed that this effect is a result of off-target activity against the VEGFR2 receptor. Increases in BP have proven to be amenable to treatment, generally without a requirement for study drug interruption. **Subjects with elevated blood pressure should receive prompt treatment.**

Blood pressure for all subjects should be kept below 140/90 mmHg; for subjects with increased cardiovascular risk or renal insufficiency, consideration should be given to maintaining the blood pressure below 130/80 mmHg. Subjects should remain on the same dose of ACEi or ARB during the dosing period (Visits 2-9). If additional anti-hypertensive therapy is required, other agents (beta-blockers, calcium channel blockers, or diuretics) should be added. In previous clinical studies evaluating fostamatinib, the following anti-hypertensive agents (alone or in combination) have proven effective in managing BP:

- Angiotensin converting enzyme inhibitors
- Angiotensin receptor blockers
- Calcium channel blockers
- Beta-blockers
- Diuretics

If aggressive and appropriate anti-hypertensive therapy does not control BP (< 140/90), it may be necessary to reduce the dose of study medication.

Management Algorithm for Elevated Blood Pressure

Follow the dose adjustment guidelines in Table 1 when adjusting the dose of study medication.

Table 1: Dose Adjustment

Starting Dose	Dose Level -1	Dose Level -2	Dose Level -3 ^a	Dose Level -4 ^a
100 mg PO bid	150 mg PO qd	100 mg PO qd	Discontinue	-----
150 mg PO bid	100 mg PO bid	150 mg PO qd	100 mg PO qd	Discontinue

^a The Sponsor's Medical Monitor should be consulted prior to consideration of dose modification to levels -3 or -4.

The following should result in prompt discontinuation of study medication:

- The blood pressure cannot be brought under control despite best efforts at blood pressure management.

If BP \geq 180/110 mmHg at any time after randomisation:

- Temporarily withhold dosing with study drug.
- Adjust anti-hypertensive medications.
- Reassess BP twice weekly.
- If a repeat BP \geq 180/110 mmHg despite adjusted anti-hypertensive treatment, permanently discontinue study drug.
- Increase anti-hypertensive medications until control is established.
- Restart study drug (at a reduced dose, see Table 1) when blood pressure $<$ 140/90 mm Hg.

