If the BP is found to be 160-179 systolic or 100-109 diastolic at any visit after randomisation:

- Continue study drug at assigned dose level.
- Adjust anti-hypertensive therapy.
- Reassess BP twice weekly.
- If, after 1 week, the BP remains \geq 160-179 systolic or \geq 100-109 diastolic despite aggressive antihypertensive therapy, interrupt study drug administration.
- Increase anti-hypertensive medications until control is established.
- Restart study drug (at a reduced dose, see Table 1) when blood pressure $<$ 140/90 mm Hg.

If BP is \geq 140 mmHg systolic and/or \geq 90 mmHg diastolic but below 160 systolic or 100 diastolic at any visit after randomisation:

- Continue study drug at assigned dose level.
- Repeat blood pressure assessment within 1 week.
- If blood pressure remains above \geq 140 mmHg systolic and/or \geq 90 mmHg diastolic after 1 week adjust antihypertensive therapy.
- Continue to monitor BP weekly until control is established.
- If BP remains \geq 140 mmHg systolic and/or \geq 90 mmHg diastolic for more than 8 weeks, despite aggressive antihypertensive therapy, reduce dose of study drug (see Table 1).

REFERENCES

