7.6.1 Adverse Events

Adverse events (AEs) will be coded using the World Health Organization Drug Dictionary (WHO-DDE), version as defined in the DMP.

Incidence for the following treatment-emergent adverse events will be summarized by system organ class, preferred term and treatment based on the safety analysis set. Subjects are counted only once within each system organ class and each preferred term.

- All TEAEs
- All TEAEs by fostamatinib dose at onset
- All TEAEs by maximum severity in the following order: severe, moderate and mild (if severity is missing, the AE will be considered as severe for summary tables and will be presented in the data listing with a missing severity)

- All TEAEs by strongest relationship to study drug in the following order: probable, possible and unlikely (the relationship to study drug will be determined by investigators). If causality is missing, the adverse event will be considered probable for summary tables but will be presented in the data listing with a missing relationship.
- Serious TEAEs
- Serious TEAEs by fostamatinib dose at onset
- TEAEs leading to discontinuation of study treatment
- TEAEs leading to discontinuation of study treatment by fostamatinib dose at onset
- TEAEs of special interest (AESI) (including—but not limited to—increases in ALT, AST, and/or total bilirubin, absolute neutrophil counts (ANC) < 1000/mm³ or 1.0 x 10⁹/L, severe diarrhea, hypertension uncontrolled by oral antihypertensive medications that recorded in dose adjustment)
- TEAEs of special interest by fostamatinib dose at onset

All AEs, serious AEs, deaths, AEs leading to discontinuation of study drug, and AEs of special interest will be listed in by-subject listings separately.

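### Appendix 1's liver hold for asymptomatic subjects depends on an undefined increase, so a confirmed high but no longer rising ALT/AST may be held late

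*Protocol*

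**What the plan says.** Appendix 1 of the protocol sorts subjects into three branches. Those meeting Hy's law stop drug and leave the study. Those with ALT/AST at least 3x ULN or bilirubin above 2x ULN plus nausea, vomiting or abdominal pain have drug withheld at once. Those with the same values and no symptoms have the tests repeated within 72 hours.

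The asymptomatic branch contains one hold instruction: "If repeat testing shows an increase in ALT/AST or total (and/or conjugated) bilirubin and the ALT/AST value exceeds" 5x ULN. The next bullet has liver tests repeated "every 3 days/72 hours until ALT/AST is decreasing, and should be followed until transaminase returns to" below 1.5x ULN. The last bullet covers restart at dose level -1 and applies only where drug was interrupted.

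Other rules in the protocol that rely on a repeat measurement are worded differently:

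- Appendix 2, neutropenia: "If repeat testing confirms that ANC is" below 1,000/µL, hold.
- Appendix 4, BP at or above 180/110: a repeat at that level "despite adjusted anti-hypertensive treatment, permanently discontinue study drug".
- Appendix 4, BP 160-179 or 100-109: "If, after 1 week, the BP remains" in that range despite treatment, interrupt.

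Where Appendix 4 wants dosing to go on, it says so: "Continue study drug at assigned dose level". Appendix 1's asymptomatic branch has no such line.

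**The concern.** The comparator for the increase is missing. If it is the previous test, the rule responds to direction before level. A subject confirmed at more than twice the 5x threshold but drifting down gets no hold instruction at that repeat, while a subject who has just crossed the threshold is held. The same fall also ends the fixed 72-hour testing, and no interval replaces it.

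Transaminase elevation is a safety parameter of particular interest (Protocol 4.4), and Section 3.5.2 reports that a very small number of patients on fostamatinib exceeded 10x ULN, so a 12x example is not fanciful. Appendix 1 requires immediate notice to the Medical Monitor only for potential Hy's law cases. About 25 sites in 8 countries (5.6) will apply the sentence, and they may not all read it alike. What is at stake is subject safety and consistent conduct.

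**Working it through.** **1. The rule under each reading.** Take an asymptomatic subject with bilirubin at or below 2x ULN. (A stable bilirubin above 2x with ALP below 2x ULN would meet Hy's law and stop drug.) The hold needs an increase in ALT/AST or bilirubin, and ALT/AST above 5x ULN.

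| ALT/AST, first then repeat (x ULN) | Bilirubin | Increase = rise over previous test | Increase = still elevated | Level rule (repeat >5x) |
|---|---|---|---|---|
| 12, 11 | flat | no hold | hold | hold |
| 12, 12 | flat | no hold | hold | hold |
| 12, 11 | rises | hold | hold | hold |
| 4.9, 5.1 | flat | hold | hold | hold |

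The results under both readings are the same whether the sentence is grouped as (ALT/AST or bilirubin increase) and >5x, or as ALT/AST increase or (bilirubin increase and >5x). A third reading, increase over baseline, also holds every row: exclusion criterion 6 keeps out ALT/AST above 1.5x ULN at Visit 1b, so a value above 5x will ordinarily be above baseline.

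**2. Which reading the text favours.** For elevation: Section 7.4 uses "Increases in ALT, AST, or bilirubin" and SAP 7.6.1 uses "increases in ALT, AST, and/or total bilirubin" in that sense. For a rise: under the elevation or baseline reading, any ALT/AST above 5x already satisfies the first condition, which then adds nothing; and the next bullet speaks of values decreasing, which is a trend. The rise reading is more natural, but the text does not settle it.

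**3. Chance of no hold, rise reading only.** The documents give no test-to-test variability, so assume independent lognormal errors with CV 5-20%.

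- Stable true level, first repeat. Each freely fluctuating marker rises with probability 1/2. No hold: ALT alone 1/2 = 0.50; ALT and bilirubin (1/2)² = 0.25; ALT, AST and bilirubin, all independent, (1/2)³ = 0.125.
- Stable true level, k repeats. No hold requires strictly descending values. ALT alone: 1/(k+1)! = 0.50, 0.167, 0.042 for k = 1, 2, 3. With bilirubin also fluctuating: (1/2!)² = 0.25, then (1/3!)² = 0.028.
- True fall from 12x to 11x, ALT alone, first repeat. The hold probability is 0.109, 0.268, 0.378 at CV 5, 10, 20%, so no hold is 0.89 down to 0.62. With bilirubin fluctuating, the hold probability is 0.555, 0.634, 0.689.
- A level rule at a true 8x or 12x holds at the first repeat with probability 0.99-1.00.

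**4. Expected number.** The documents give no rate above 5x ULN; assume 1-5%. Treat every such subject as stable, asymptomatic and outside Hy's law, which overstates the count.

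- Cohort 2 (25 on 150 mg bid), first repeat: 25 × 0.01 × 0.125 = 0.03 to 25 × 0.05 × 0.50 = 0.63. The upper figure falls to 25 × 0.05 × 0.167 = 0.21 after two repeats and 25 × 0.05 × 0.042 = 0.05 after three.
- All 50 fostamatinib subjects, first repeat: 50 × 0.01 × 0.125 = 0.06 to 50 × 0.05 × 0.50 = 1.25. The upper figure falls to 0.42, then 0.10.
- Worst corner for Cohort 2 (5% rate, every case slowly falling, bilirubin flat, CV 5%): 25 × 0.05 × 0.891 = 1.1 at the first repeat.

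**5. Length of the delay.** While values stay flat, 72-hour repeats continue. Once they fall, the next fixed test is the next scheduled visit. Study days from SAP Section 10: 126 - 84 = 42 and 168 - 126 = 42 days between visits. With the ±7-day windows at Weeks 18 and 24: (168 + 7) - (126 - 7) = 56. Extended treatment (Table 3): 12 × 7 = 84 days. A repeat at 72 hours uses up 3 of these days.

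**The case against.** The best defence is that nothing obliges a site to keep dosing. A reader might infer from 12x then 11x that the protocol directs continued treatment, or that the subject is never held. The documents support neither. Appendix 1 is a guideline and is silent on that case. Section 7.4 separately allows modification for severe or life-threatening related events; 7.9 allows withdrawal for an adverse event on the investigator's judgement; the Medical Monitor (5.4) and the Safety Review Committee (5.5) review safety. The hold is not limited to the first repeat, and follow-up to below 1.5x ULN is required, so a later rise above 5x still triggers it. The long gaps arise only if a site orders nothing between visits despite that instruction. All of this stands, and it limits the consequence to delay.

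It is also fair that two of three readings close the gap, and that 3.5.2 calls enzyme rises mostly mild to moderate. What survives is that the reading the sentence most naturally bears gives the higher confirmed level the weaker written response, and that the safeguards rest on judgement where the neutropenia and BP rules are explicit.

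A reader might further infer that the symptomatic branch wrongly holds drug for an isolated unconjugated bilirubin rise. The Note at the head of Appendix 1 already says not to hold for that, and it can be taken to govern every branch.

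**Conclusion.** The point holds as a minor safety-wording defect. Confidence is high that the comparator is missing; whether sites would act on the rise reading cannot be told from the documents. On that reading, a stable level far above 5x ULN has a 0.125-0.50 chance of no hold instruction at the first repeat, under the assumed error model, and that chance drops quickly with further tests. On the other readings it is zero. The expected number in Cohort 2 is likely well below one subject (0.03-0.63 at the first repeat for stable levels); it passes one only with every assumption at its worst. The event rate, CVs and independence are assumptions, not document figures. The harm is a possible delay to a hold, longest where values have begun to fall and visits are 42 or 84 days apart. The primary analysis is unaffected.

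**What to change.** Replace the asymptomatic hold with: *hold study drug if any repeat test shows ALT/AST >5x ULN, whether or not it has risen since the previous test.* Under the usual grouping of the sentence, this keeps every hold the present rule gives, including 4.9x then 5.1x, and adds 12x then 11x. Add a follow-up interval, for example weekly, from when values start to fall until they are below 1.5x ULN.

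The cost is one reworded bullet and one interval, carried in the next amendment, with the IEC/IRB approval that Section 11.2 requires before use. Cohort 1 has finished the main study, so the benefit is to Cohort 2 and to extended treatment, where Section 7.11 applies the same dose-adjustment rules. The downside is a few extra liver tests and a few extra interruptions. Restart is at dose level -1 and 7.4 bars later re-escalation, so each interruption that leads to restart carries a lasting cut in daily dose: (300 - 200)/300 = 33% from 150 mg bid, or (200 - 150)/200 = 25% from 100 mg bid.

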6.2 Exclusion Criteria

1. History of or active, clinically significant, respiratory, gastrointestinal (including pancreatitis), hepatic, neurological, psychiatric, musculoskeletal, genitourinary, dermatological, or other disorder that, in the Investigator's opinion, could affect the conduct of the study or the absorption, metabolism or excretion of the study drug.
2. Have had any major cardiovascular event within the 180 days prior to randomisation, including but not limited to: myocardial infarction, unstable angina, cerebrovascular accident, pulmonary embolism, or New York Heart Association Class III or IV heart failure.
3. Diagnosis or history suggestive of Henoch-Schonlein purpura.
4. Estimated glomerular filtration rate (eGFR) < 30 mL/min/1.73 m² (using the MDRD equation) at the time of Screening (Visit 1b).
Note: Values as low 25 mL/min/1.73 m² may be permitted with prior written permission from the Rigel Medical Monitor if, according to the Investigator, there has been no clinically significant recent change in renal status.
5. A 50% decrease in eGFR from most recent pre-study clinic visit to Visit 1b.
6. An absolute neutrophil count of $< 1,500/\mu\text{L}$, Hgb < 9 g/dL, ALT or AST of $> 1.5x$ ULN, total bilirubin > 2.0 mg/dL at Visit 1b. The Investigator may reassess these laboratory abnormalities within 30 days after Screening (Visit 1b).
7. Acute gastrointestinal symptoms (eg, nausea, vomiting, diarrhoea) at Baseline (Visit 2). The subject may be reassessed after full recovery from the acute gastrointestinal illness.
8. Active bacterial or parasitic infections, including tuberculosis.
9. Serologic results suggestive of active hepatitis B or hepatitis C (subjects may be included if confirmed hepatitis C recombinant immunoblot assay negative or hepatitis C virus RNA negative [qualitative]), or subjects with suspected human immunodeficiency virus (HIV).

10. Use within 6 months prior to pre-study renal biopsy of cyclophosphamide, mycophenolate mofetil, azathioprine, or Rituximab (or other anti-B cell therapies). Those subjects who had been treated with an anti- B cell therapy must have a normal CD19 count by Visit 1b.
11. Use of > 15 mg/day prednisone (or other corticosteroid equivalent). For those subjects taking corticosteroids for renal indication, the daily dose should not change from Baseline (Visit 2) to the end of the study drug treatment (Visit 9).
12. Prior or current use of cyclosporine or tacrolimus.

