Appendix 1: Guideline for Dose Modification for Possible Drug-Induced Liver Injury (DILI): AST or ALT 3x ULN or TBL > 2xULN

The Investigator is responsible for determining whether the subject meets Hy’s law criteria for severe liver injury: aspartate aminotransferase (AST) or alanine aminotransferase (ALT) \geq 3x upper limit of normal (ULN) plus total bilirubin (TBL) > 2x ULN and alkaline phosphatase (ALP) < 2x ULN.

- **Note:** Fostamatinib is an inhibitor of UGT1A1, the enzyme responsible for the glucuronidation of bilirubin; occasionally an isolated increase in total and unconjugated (indirect) bilirubin may be observed. Study drug should not be held for an isolated increase in total and unconjugated (indirect) bilirubin.
- The study Medical Monitor should be notified immediately of any potential case meeting Hy’s law criteria.

Table 1: Dose Adjustment

Starting Dose	Dose Level -1	Dose Level -2	Dose Level -3 ^a	Dose Level -4 ^a
100 mg PO bid	150 mg PO qd	100 mg PO qd	Discontinue	-----
150 mg PO bid	100 mg PO bid	150 mg PO qd	100 mg PO qd	Discontinue

^a The Sponsor’s Medical Monitor should be consulted prior to consideration of dose modification to levels -3 or -4.

Identification

If AST or ALT \geq 3x ULN and total (and/or conjugated) bilirubin > 2x ULN, with ALP < 2x ULN (Hy’s law criteria met), the Investigator should follow the instructions below:

- Stop study drug treatment immediately and withdraw the subject from the study for possible drug-induced liver injury.
- Complete the appropriate LFT module of the case report form (CRF) with the original laboratory test results.
- Follow the subject until liver biochemistry parameters and any clinical symptoms and signs return to normal or baseline levels, or as long as medically indicated.
- Investigate the etiology of the event and perform diagnostic investigations as discussed with the Sponsor’s Medical Monitor.

If AST or ALT \geq 3x ULN or total (and/or conjugated) bilirubin > 2x ULN, and the subjects are exhibiting the following symptoms: nausea, vomiting, abdominal pain:

- Withhold/ interrupt dosing with study drug immediately.
- Repeat LFTs, including bilirubin and alkaline phosphatase every 3 days/72 hours until ALT/AST or total (and/or conjugated) bilirubin returns to < 1.5x ULN.

- Complete the appropriate LFT module of the CRF with the original laboratory test result.

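### Appendix 1 joins ALT/AST and bilirubin with *or* in its restart rule, so, read literally, bilirubin recovery alone can lift a liver-test hold while ALT/AST is still raised

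*Protocol*

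**What the plan says.** Protocol Section 7.4 refers liver-test dose changes to Appendix 1 and adds no restart condition of its own. Section 7.11 applies the same rules in extended treatment. Appendix 1 has three branches.

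- **Hy's law** (ALT or AST at least 3x ULN, bilirubin above 2x ULN, ALP below 2x ULN): "Stop study drug treatment immediately and withdraw the subject from the study for possible drug-induced liver injury". There is no restart.
- **Symptomatic** (ALT/AST at least 3x or bilirubin above 2x ULN, with abdominal pain, nausea or vomiting): drug is held at once and liver tests are repeated "every 3 days/72 hours until ALT/AST or total (and/or conjugated) bilirubin returns to < 1.5x ULN". Then: "When the ALT/AST or total (and/or conjugated) bilirubin returns to $< 1.5x$ ULN, study drug may be restarted at dose level -1".
- **Asymptomatic** (same thresholds, no symptoms): tests are repeated within 72 hours. The hold rule is: "If repeat testing shows an increase in ALT/AST or total (and/or conjugated) bilirubin and the ALT/AST value exceeds $5x$ ULN, hold dosing". Testing goes on "until ALT/AST is decreasing, and should be followed until transaminase returns to $< 1.5x$ ULN". For held subjects, "upon return of ALT/AST or total (and/or conjugated) bilirubin to $< 1.5x$ ULN, study drug may be restarted at dose level -1".

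A note at the top of the appendix, written because the drug inhibits UGT1A1, adds: "Study drug should not be held for an isolated increase in total and unconjugated (indirect) bilirubin". It governs the hold and is silent on restart.

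**The concern.** The other management guidelines tie restart to the parameter that caused the hold: ANC above 1,500/µL in Appendix 2, diarrhoea at Grade 1 or less in Appendix 3, blood pressure below 140/90 mmHg in Appendix 4. Appendix 1 instead offers two alternatives, and either one is enough. In the asymptomatic branch no hold can occur without ALT/AST above 5x ULN, yet bilirubin can release it. The transaminase follow-up line in that branch is a monitoring duty and is not made a condition of restart. The symptomatic branch has no such line.

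The stake is re-dosing while the liver signal is still present and, in the symptomatic branch, an early end to close testing. Transaminase elevation is singled out as a safety parameter in Section 4.4, and Section 3.5.2 reports a very small number of elevations above 10x ULN in the programme.

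**Working it through.** No plan figure is at issue, so the check is one of logic, supported by simple arithmetic. The triggers, hold rules and restart rules are those of Appendix 1. The laboratory values are illustrative assumptions in multiples of ULN; the documents give no event rate for this situation.

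**1. Can both markers be raised in a held subject who is not a Hy's law case?** Yes, in two ways: bilirubin from 1.5x to 2x, or bilirubin above 2x with ALP at least 2x.

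**2. The rule as written, against a rule requiring both markers below 1.5x:**

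| Branch | At hold: ALT, bilirubin, ALP | Later: ALT, bilirubin | As written | Both required |
|---|---|---|---|---|
| Symptomatic | 4, 1.8, 1 | 4, 1.4 | restart allowed | refused |
| Symptomatic | 4, 2.5, 2.5 | 4, 1.4 | restart allowed | refused |
| Asymptomatic | 6, 1.8, 1 | 6, 1.4 | restart allowed | refused |
| Asymptomatic | 6, 2.5, 2.5 | 6, 1.4 | restart allowed | refused |
| Hy's law | 6, 2.5, 1 | n/a | withdrawn | withdrawn |

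**3. Re-apply the triggers after release.**

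- *Symptomatic, ALT 4x.* Still at least 3x. If symptoms persist, drug is held again. If they have gone, the asymptomatic branch requires a repeat within 72 hours and follow-up to below 1.5x. Testing does not lapse.
- *Symptomatic, ALT down to 2.5x, bilirubin 1.4x.* Neither trigger is met. Restart is allowed and the 72-hour tests may end with ALT at 2.5/1.5 = 1.67 times the release line. The next scheduled chemistry can be 6 weeks away late in the main study (Weeks 12, 18, 24), or 12 weeks (±2) in extended treatment.
- *Asymptomatic, ALT from 6x to 5.5x, bilirubin from 1.6x to 1.4x.* Restart is allowed at 5.5/1.5 = 3.7 times the line. Follow-up continues, but a new hold needs a rise in ALT/AST or bilirubin with ALT/AST above 5x. A falling ALT does not supply it.

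**4. Narrower reading.** Suppose a marker can return only if it crossed its own trigger. For one trigger marker to release the hold while the other is unrecovered, both must have triggered: ALT/AST at least 3x and bilirubin above 2x. With ALP below 2x that is Hy's law. The gap is then confined to ALP at least 2x ULN.

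**5. Which limb is easier to meet?** Fall needed to reach 1.5x from x: 1 − 1.5/x.

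- Bilirubin: 1.6x, 6.25%; 1.8x, 16.7%; 2.0x, 25%; 2.5x, 40%; 3.0x, 50%.
- ALT/AST: 3x, 50%; 4x, 62.5%; 5x, 70%; 6x, 75%.

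With ALT/AST at least 3x and ALP below 2x, bilirubin cannot exceed 2x without meeting Hy's law, so its limb needs a fall of about 25% at most, against at least 50% for ALT/AST. That bound does not apply when ALP is at least 2x, or when bilirubin alone triggered a symptomatic hold.

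**The case against.** The best defence is that the restart clause repeats the pairing in the triggers, so *or* means whichever marker caused the hold. That is a natural reading, and step 4 shows that it leaves only a narrow corner. But the text does not say it, and a site following the sentence as written would not be in breach.

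The safeguards are also real. Restart is permitted, not required. Dose level -1 cuts the daily dose from 300 to 200 mg (67%) or from 200 to 150 mg (75%). The Medical Monitor and the Safety Review Committee review safety. These limit the harm, but none makes transaminase recovery a restart condition, and the Table 4 footnote calls for consultation only before levels -3 and -4.

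Five stronger inferences are tempting, and the documents do not support them:

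- *A subject whose bilirubin was never raised could restart at once.* The sentences speak of a return, which implies an earlier rise.
- *Testing stops with ALT near 4x ULN.* Step 3 shows that such a subject re-enters a branch.
- *Restart above the entry limit is itself a defect.* Exclusion criterion 6 does bar "ALT or AST of $> 1.5x$ ULN, total bilirubin > 2.0 mg/dL at Visit 1b". On treatment, however, the plan lets asymptomatic subjects at 3x to 5x ULN continue at the assigned dose, so the entry limit is a weak comparator.
- *A bilirubin fall during a hold is only drug washout.* Section 3.5.2 describes UGT1A1 inhibition, but no bilirubin time course is given. The point does not rest on this.
- *Hy's law cases may be re-dosed.* They are withdrawn.

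Rarity also counts. Section 3.5.2 reports 5 patients across the programme meeting criteria for potential drug-induced liver injury, one without simultaneous elevations; Section 3.1 puts RA exposure above 3,000 patient-years. This is not a count of the present situation, since it would miss bilirubin between 1.5x and 2x, but it suggests few cases among about 50 subjects on active drug.

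**Conclusion.** The concern holds as a minor safety-wording correction, a cheap improvement. On the literal reading, bilirubin recovery alone can lift a hold in both non-Hy's-law branches. What the rest of the algorithm leaves uncovered is (a) asymptomatic subjects with high but falling ALT/AST, who may be re-dosed under continued follow-up, and (b) symptomatic-branch subjects with ALT/AST between 1.5x and 3x ULN, whose 72-hour tests may also end. On the narrower reading it is only the combination of ALT/AST at least 3x, bilirubin above 2x and ALP at least 2x ULN. The logic follows from the text; the example values are assumed and the number of subjects affected is unknown but probably small. Nothing here bears on the efficacy analysis.

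**What to change.** Replace both restart sentences with wording to this effect:

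> When ALT and AST are both < 1.5x ULN and, if conjugated bilirubin was raised at the hold, it has also come back to < 1.5x ULN, dosing may resume at dose level -1. A remaining isolated unconjugated (indirect) rise, with total bilirubin raised for that reason alone, does not prevent restart.

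Use the same condition to end the symptomatic 72-hour tests. Naming conjugated bilirubin keeps the UGT1A1 exception and avoids a conflict when transaminases recover but unconjugated bilirubin stays above 2x ULN. Direct and indirect bilirubin are already in the chemistry panel.

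The cost is three sentences in Appendix 1, some slightly longer holds and a few more liver tests. Sample size, scheduled visits and analysis are unchanged. Section 11.2 requires IEC/IRB approval of any amendment, at about 25 sites in 8 countries, so the change should be bundled with the next one. Section 10.9 shows that Cohort 1 data through Week 26 have already been analysed, so the benefit falls to remaining Cohort 2 subjects and those in extended treatment.
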